3.4.4.2 Serious Adverse Events

A serious adverse event is a sign, symptom or medical condition which:

- is fatal or life-threatening
- results in persistent or significant disability/incapacity
- constitutes a congenital anomaly/birth defect
- requires inpatient hospitalization or prolongation of existing hospitalization, unless hospitalization is for:
 - routine treatment or monitoring of the studied indication, not associated with any deterioration in condition
 - elective or pre-planned treatment for a pre-existing condition that is unrelated to the indication under study and has not worsened since the start of study drug
 - treatment on an emergency outpatient basis for an event not fulfilling any of the definitions of a SAE given above and not resulting in hospital admission

- social reasons and respite care in the absence of any deterioration in the patient's general condition
- is medically significant, i.e., defined as an event that jeopardizes the patient or may require medical or surgical intervention to prevent one of the outcomes listed above

Reporting of Serious Adverse Events:

To ensure patient safety, every SAE, **regardless of suspected causality**, occurring

- after the patient has provided informed consent and until 4 weeks after the patient has stopped study treatment/participation
- after the patient is randomized and until 4 weeks after the patient has stopped study treatment
- after the patient begins taking study drug and until 4 weeks after the patient has stopped study treatment
- after protocol-specified procedures begin (e.g., placebo run-in, washout period, double-blind treatment, etc.) and until 4 weeks after the patient has stopped study treatment
- after the start of any period in which the study protocol interferes with the standard medical treatment given to a patient (e.g., treatment withdrawal during washout period, change in treatment to a fixed dose of concomitant medication) and until 4 weeks after the patient has stopped study treatment

must be reported to Novartis within 24 hours of learning of its occurrence. Any SAEs experienced after this 4-week period should only be reported to Novartis if the investigator suspects a causal relationship to the study drug. Recurrent episodes, complications, or progression of the initial SAE must be reported as follow-up to the original episode within 24 hours of the investigator receiving the follow-up information. An SAE occurring at a different time interval or otherwise considered completely unrelated to a previously reported one should be reported separately as a new event.

The investigator must assess and record the relationship of each SAE to each specific study drug (if there is more than one study drug), complete the SAE Report in English, and send the completed, signed form by [contact]) within 24 hours to the Novartis Drug Safety and Epidemiology Department.

The original copy of the SAE Report and the fax confirmation sheet must be kept within the Trial Master File at the study site.

Follow-up information is sent to the same person to whom the original SAE Report Form was sent, using a new SAE Report Form stating that this is a follow-up to the previously reported SAE and giving the date of the original report. Each re-occurrence, complication, or progression of the original event should be reported as a follow-up to that event regardless of when it occurs. The follow-up information should describe whether the event has resolved or continues, if and how it was treated, whether the blind was broken or not (if applicable), and whether the patient continued or withdrew from study participation.

If the SAE is not previously documented in the Investigator's Brochure or Package Insert (new occurrence) and is thought to be related to the Novartis study drug, a Drug Safety and Epidemiology Department associate may urgently require further information from the investigator for Health Authority reporting. Novartis may need to issue an Investigator Notification (IN), to inform all investigators involved in any study with the same drug that this SAE has been reported. Suspected Unexpected Serious Adverse Reactions (SUSARs) will be collected and reported to the competent authorities and relevant ethics committees in accordance with Directive 2001/20/EC or as per national regulatory requirements in participating countries.

3.4.5 Novartis instructions for rapid notification of serious adverse events

The principal investigator has the obligation to report all serious adverse events to the FDA, IRB, and Novartis Pharmaceuticals Drug Safety and Epidemiology Department (DS&E).

All events reported to the FDA by the investigator are to be filed utilizing the Form FDA 3500A (MedWatch Form).

All events must be reported, by [contact]), to Novartis Pharmaceuticals DS&E Department within 24 hours of learning of its occurrence. This includes serious, related, labeled (expected) and serious, related, unlabeled (unexpected) adverse experiences. All deaths during treatment or within 30 days following completion of active protocol therapy must be reported within 5 working days.

Any serious adverse event occurring after the patient has provided informed consent and until 4 weeks after the patient has stopped study participation must be reported. This includes the period in which the study protocol interferes with the standard medical treatment given to a patient (e.g. treatment withdrawal during washout period, change in treatment to a fixed dose of concomitant medication).

Serious adverse events occurring more than 4 weeks after study discontinuation need only be reported if a relationship to the Novartis study drug (or therapy) is suspected.

For Comparator Drugs/Secondary Suspects (Concomitant Medications), all serious adverse experiences will be forwarded to the product manufacturer by the investigator.

3.4.6 Pregnancy and assessments of fertility for Everolimus

There are no adequate data from the use of everolimus in pregnant women. Studies in animals have shown reproductive toxicity effects including embryo-toxicity and fetotoxicity. The potential risk for humans is unknown. Everolimus should not be given to pregnant women unless the potential benefit outweighs the potential risk to the fetus. If a pregnancy occurs while on study treatment, the newborn will be followed for at least 12 months.

It is not known whether everolimus is excreted in breast milk. However, in animal studies, everolimus and/or its metabolites readily passed into the milk of lactating rats. Women taking everolimus should therefore not breast-feed.

Women of childbearing potential

Women of child-bearing potential, defined as all women physiologically capable of becoming pregnant, must use highly effective contraception during the study and for 8 weeks after stopping treatment. Highly effective contraception is defined as either:

- Total abstinence: When this is in line with the preferred and usual lifestyle of the subject. [Periodic abstinence (e.g., calendar, ovulation, symptothermal, post-ovulation methods) and withdrawal are not acceptable methods of contraception]
- Sterilization: have had surgical bilateral oophorectomy (with or without hysterectomy) or tubal ligation at least six weeks before taking study treatment. In case of oophorectomy alone, only when the reproductive status of the woman has been confirmed by follow up hormone level assessment
- Male partner sterilization (with the appropriate post-vasectomy documentation of the absence of sperm in the ejaculate). [For female subjects on the study, the vasectomised male partner should be the sole partner for that subject].
- Use of a combination of any two of the following (a+b or a+c or b+c):
 - a. Use of oral, injected, implanted or other hormonal methods of contraception
 - b. Placement of an intrauterine device (IUD) or intrauterine system (IUS)
 - c. Barrier methods of contraception: Condom or Occlusive cap (diaphragm or cervical/vault caps) with spermicidal foam/gel/film/cream/vaginal suppository
- In case of use of oral contraception, women should have been stable on the oral agent before taking study treatment.

Male Contraception

Sexually active males must use a condom during intercourse while taking the drug and for 8 weeks after stopping treatment and should not father a child in this period.

A condom is required to be used also by vasectomised men in order to prevent delivery of the drug via seminal fluid.

Female partners of male patients must also be advised to use one of the following contraception methods: Use of (1) oral, injected, implanted or other hormonal methods of contraception, or (2) intrauterine device (IUD) or intrauterine system (IUS), or (3) prior male/female sterilization.

Fertility

The potential for everolimus to cause infertility in male and female patients is unknown. However, menstrual irregularities, secondary amenorrhea and associated luteinizing hormone (LH)/follicle stimulating hormone (FSH) imbalance has been observed. Based on non-clinical findings, male and female fertility may be compromised by treatment with everolimus.

Pregnancy Reporting

Preclinical data regarding reproductive toxicity is described in the most recent Investigator Brochure. The potential reproductive risk for humans is unknown. Women of childbearing potential should be advised to use highly effective contraception methods while they are receiving everolimus and up to 8 weeks after treatment has been stopped.

To ensure patient safety, each pregnancy occurring while the patient is on study treatment must be reported to Novartis within 24 hours of learning of its occurrence. The pregnancy should be followed up to determine outcome, including spontaneous or voluntary termination, details of the birth, and the presence or absence of any birth defects, congenital abnormalities, or maternal and/or newborn complications. The newborn will be followed for at least 12 months.

Pregnancy should be recorded on a Clinical Trial Pregnancy Form and reported by the investigator to the oncology Novartis Drug Safety and Epidemiology Department (DS&E). Pregnancy follow-up should be recorded on the same form and should include an assessment of the possible relationship to the study treatment and any pregnancy outcome. Any SAE experienced during pregnancy must be reported on the SAE Report Form.

4 Protocol amendments, or changes in study conduct

Any change or addition (excluding administrative) to this protocol requires a written protocol amendment that must be reviewed by Novartis and the investigator and approved by the IRB before implementation. Amendments significantly affecting the safety of subjects, the scope of the investigation or the scientific quality of the study require additional approval by the IRB. A copy of the written approval of the IRB must be provided to Novartis.

5 Data Management

5.1 Data Collection

Investigators must record the information required by the protocol.

5.2 Data Safety and Monitoring Plan

The CRO website link describing the CRO monitoring plans can be found here:

http://cro.onc.jhmi.edu/news/SKCCC_DSMP.doc

Internal Monitoring Plan

The PI will review data to assure the validity of data, as well as, the safety of the subjects. The PI will monitor the progress of the trial, review safety reports and clinical trial efficacy endpoints –on an ongoing basis to confirm that the safety outcomes favor continuation of the study.

The PI will be responsible for maintaining the clinical protocol, timely reporting of adverse events, assuring that consent is obtained and documented, reporting of unexpected outcomes, and reporting the status of the trial in the annual report submitted to the IRB and to the Safety Monitoring Committee per the SKCCC Data and Safety Monitoring Plan.

External Monitoring Plan

This is a DSMP Level I study under the SKCCC Data Safety Monitoring Plan (9/22/2011). The Clinical Research Office QA Group will perform an audit after the first subject has been treated and then periodically depending on the rate of accrual and prior audit results. All trial monitoring and reporting will be reviewed by the SKCCC Safety Monitoring Committee in accordance with the Data and Safety Monitoring Plan and IRB policies.

6.0 Statistical Considerations

This is a study of maintenance rituximab with mTor inhibition (everolimus) after high-dose consolidative therapy in CD20+, B-cell Lymphomas and Hodgkin's Lymphoma. It is hypothesized that the addition of new agents in patients with minimal residual disease will improve event free survival and that everolimus may act synergistically with rituximab.

Primary Objective:

To determine the safety of maintenance rituximab and prolonged mTOR inhibition with everolimus in CD20+, B cell lymphoma and Hodgkin's Lymphoma after high-dose consolidative therapy.

Secondary Objectives:

1. The secondary endpoint of this study is to evaluate event-free survival (EFS) at three years. EFS is defined as the interval from registration to the date of first objective disease progression, death from any cause, or last patient evaluation. Patients who have not progressed or died will be censored at the last date they were assessed and deemed relapse-free.
2. To determine whether maintenance rituximab with everolimus treatment reduces the frequency circulating cancer cells.
3. To determine if relapsed disease is sensitive, in-vivo, to mTor kinase inhibition.

Study Design:

Treatment will consist of rituximab 375mg/m² q 90 days (4 infusions) with everolimus 2.5 mg orally daily for one year. There will be no drug escalation in this study however serum drug levels will be monitored and the level of everolimus will be maintained in the therapeutic window. For patients outside the range of 3 – 15ng/mL and not experiencing grade 3 or higher toxicity, the dose will either be increased or decreased by 2.5mg per day to bring patients within range, down to 2.5 mg every 4 days. Addendum 4 provides details on dose adjustments and treatment holds. For patients experiencing grade 3 or higher toxicities adjustments will be made as detailed in addendum 4. The study will be monitored continuously for safety.

Sample size/Accrual Rate:

The accrual rate for this study is expected to be 20 patients per year. The safety objective of this trial is based on the precision of estimating grade 3 or higher toxicities. Sixty patients will allow us to estimate the proportion of patients experiencing grade 3 or higher toxicities with a precision of $\pm 13\%$.

Early Stopping Guideline for Safety:

Because dose will be managed to target a therapeutic window, toxicity evaluation in this study will be based on events that would indicate either the therapeutic dose was too toxic to maintain or that this method increased the probability of unexpected complications. These events include any patient for which the minimum 2.5 mg everolimus every other day was not tolerable or any unexpected hospitalizations during protocol participation. We will monitor the study continuously. If it becomes evident that the proportion of failures convincingly exceeds 15%, the study will be halted for a safety consultation. The stopping rule will hold enrollment if the posterior probability of failure being larger than 0.15 is 75% or higher. The prior for this monitoring rule is beta(1, 6). This means that our prior guess at the proportion of failures is 14.3%, and there is 90% probability that this proportion is between 0.85% and 39%.

Stop if	2AEs	3AEs	4AEs	5AEs	6AEs	7AEs	8AEs	9AEs	10AEs	11AEs	12AEs
in N	2-5	6-11	12-16	17-22	23-28	29-34	35-40	41-46	47-52	53-58	59-60

The next table shows the percent of the time that the stopping rule will terminate the study under different hypothetical risks of AEs, along with the average sample size (based on 5000 simulations).

Risk of AE	0.05	0.10	0.15	0.20	0.25	0.30	0.35
% of Time Study Stops	3.2%	18.5%	49.7%	79.4%	95.2%	99.2%	99.9%
Expected Sample Size	58.3	51.2	38.6	25.4	16.1	10.9	8.0

Early Stopping Guideline for Futility and Simulation Sample Size:

This study will be monitored for efficacy as well as toxicity. If the study meets the accrual goal of 20 patients per year, accrual would be completed by the time the first patients enrolled on study reach the three year efficacy endpoint. We will therefore monitor the study based on one-year EFS, knowing that if the one-year EFS is convincingly less than our targeted EFS at three years, the study would not meet its efficacy objective and the trial should be halted. Patients that have not progressed or died will be censored at the last date they were assessed and deemed relapse-free.

The non-parametric Kaplan-Meier estimate will be used to estimate the EFS function at one year. After 20 patients have been enrolled, the design will include interim analyses for futility that could halt the trial if it seems likely that the drug combination does not have sufficient clinical activity.

The sample size of 60 and the study design operating characteristics assume a three-year recruitment period with an additional follow-up of one year. Based on a study of high dose cyclophosphamide and rituximab without stem cell transplantation at our institution [2], the one and three-year EFS for low grade B cell lymphomas was 67 and 49% respectively. The simulation below demonstrates how the operating characteristics of the design varies when the uncertainty of the one-year EFS is characterized with the prior: beta(3,2). This implies that our prior guess at one-year EFS for these patients is 60%, and there is 90% probability that the EFS at 12 months is between 25% and 90%.

We have designed this study to stop early only if it appears that this treatment is associated with a lower one-year EFS than 50%. Specifically, the stopping rule will hold enrollment if the posterior probability of one-year EFS being less than 50% is 70% or higher. Simulations were carried out with exponential survival and staggered patient entry. We assumed, on average, 2 patients would enter the study per month. Interim analyses began once 20 patients entered the study and occurred after groups of 10 patients thereafter, up to a maximum of 60 patients. The interim analysis estimates of one-year EFS are based on analyses with an underlying Dirichlet process prior. We approximated the posterior distribution, which is actually a mixture of Beta distributions, the mixture depending on the amount of censoring, with a single Beta distribution. The parameters of this posterior Beta distribution are based on the number of failures and the effective sample size at 12 months, combined with the parameters of the prior. The following tables summarize the operating characteristics under various scenarios for the underlying exponential EFS, based on 1000 simulations. The 95% posterior intervals are the quantiles of

the simulated one-year EFS corresponding to probabilities of .025 and .957. The interpretation is that the posterior probability that the estimate of one-year PFS lies in this interval is 95%.

Prior is beta(3,2) : Mean is 0.60

1-yr EFS	Prob Stop for Futility	Avg N	Est 1- yr PFS	Lo 95% Post Int'l	Hi 95% Post Int'l	Prob H0 Rejected
0.45	0.60	40.3	0.42	0.25	0.58	0.03
0.5	0.37	47.7	0.47	0.25	0.62	0.12
0.55	0.17	54.1	0.53	0.35	0.67	0.28
0.60	0.07	57.5	0.59	0.40	0.72	0.57
0.65	0.02	59.1	0.64	0.50	0.77	0.83
0.70	0.01	59.8	0.70	0.58	0.82	0.96

Analysis of primary objective:

The proportion of patients positive for the toxicity evaluation as defined for this study: patients for which the minimum 2.5 mg everolimus every other day was not tolerable or any unexpected hospitalizations during protocol participation will be reported with an exact binomial calculation and 95% confidence interval. The proportion of patients requiring dose adjustments down as well as the proportion requiring dose adjustments up will be reported separately with confidence intervals. All other grade 1 and 2 toxicities will be reported by type and grade, overall and within intervals throughout the study (0, 60], (60, 90], (90,120], (120, 180], (180, 365] and (365, 1460].

Analysis of secondary objectives:

Standard life table methods will be used to analyze EFS. We will report the one and three-year EFS with 95% confidence intervals. The three-year EFS will be compared to the null EFS of 49% with a Z-score and a one-sided alpha level of 0.05.

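### The safety stopping table assumes each outcome is known at entry and the plan never defines N, so the stated stopping percentages and expected sample sizes are not those of a trial with one-year treatment

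*Combined protocol and SAP*

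**What the plan says.** All references are to section 6.0, Statistical Considerations, of the combined protocol and SAP.

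- **Early Stopping Guideline for Safety.** A failure is a patient who cannot tolerate the stated minimum everolimus dose "or any unexpected hospitalizations during protocol participation. We will monitor the study continuously". The rule: "The stopping rule will hold enrollment if the posterior probability of failure being larger than 0.15 is 75% or higher". The prior is beta(1, 6). A boundary of AEs in N follows, for N from 2 to 60, and then a table of stopping percentages and expected sample sizes from 5000 simulations, introduced as follows: "The next table shows the percent of the time that the stopping rule will terminate the study under different hypothetical risks of AEs".
- **Study Design and Sample size/Accrual Rate.** Treatment is rituximab "with everolimus 2.5 mg orally daily for one year". "The accrual rate for this study is expected to be 20 patients per year".
- **Early Stopping Guideline for Futility.** Here the entry and event model is stated: "Simulations were carried out with exponential survival and staggered patient entry". "We assumed, on average, 2 patients would enter the study per month". The effective sample size there allows for censoring.

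The safety text gives no entry or event-time model. It does not say whether N means patients enrolled, patients fully followed, or something in between.

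**The concern.** A patient who entered last month has not yet had the chance to fail that a patient with a year on treatment has had. At 20 entries per year and one year of treatment, about 20 × 1 = 20 patients can be part-way through at any time. A rule that compares failures with N therefore depends on how these patients are counted, and a table that ignores them describes a different trial.

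Safety is the primary objective, and this table is what the IRB and the Safety Monitoring Committee have for judging how many patients would be exposed before a hold. The undefined N also matters in use. Take an invented example: 20 enrolled, 4 failures (2 of them past one year), and 6 others who have completed a year without failure.

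- N = enrolled: 4 in 20; the boundary is 5; no hold.
- Failures at once, others when complete: 4 in 4 + 6 = 10; the boundary is 3; hold.
- Completed patients only: 2 in 2 + 6 = 8; the boundary is 3; no hold.

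The same data give different decisions.

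**Working it through.** **Inputs from section 6.0:** prior beta(1, 6); hold if P(failure rate > 0.15 | data) ≥ 0.75; maximum N 60; 20 entries per year; one year of treatment.

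**Assumed, because the documents give nothing:** Poisson entry; failure times uniform over 30, 90, 180 or 365 days; one-year follow-up.

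**1. Boundary.** After k failures in n patients the posterior is beta(1 + k, 6 + n − k). For 2 in 5, P(beta(3, 9) > 0.15) = 0.779, which is at least 0.75, so hold. For 2 in 6, P(beta(3, 10) > 0.15) = 0.736, so continue. This gives the printed range of 2–5 for two events. The whole boundary agrees at every N from 2 to 60.

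**2. The plan's table.** An exact binomial recursion, checking the boundary after each patient as if the outcome were known at entry, gives:

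| Risk | Stated stop % | Exact stop % | Stated N | Exact N |
|---|---|---|---|---|
| 0.05 | 3.2 | 3.5 | 58.3 | 58.2 |
| 0.10 | 18.5 | 19.2 | 51.2 | 51.0 |
| 0.15 | 49.7 | 50.2 | 38.6 | 38.4 |
| 0.20 | 79.4 | 80.0 | 25.4 | 25.4 |
| 0.25 | 95.2 | 94.9 | 16.1 | 16.2 |
| 0.30 | 99.2 | 99.2 | 10.9 | 10.9 |
| 0.35 | 99.9 | 99.9 | 8.0 | 8.0 |

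The differences are within simulation error. Both printed rows are the instant-outcome result.

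**3. Staggered entry, same boundary.** 10,000 or more trials per scenario. Mean N is the number enrolled at the hold, or 60 if there is no hold during accrual. Results for two risks:

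| Reading of N | Failure timing | Risk 0.20: hold in accrual / ever cross / mean N | Risk 0.25: hold in accrual / ever cross / mean N |
|---|---|---|---|
| Stated in plan | – | 79.4% / 25.4 | 95.2% / 16.1 |
| Enrolled | within 30 days | 78% / 78% / 27 | 94% / 94% / 18 |
| Enrolled | within 90 days | 73% / 74% / 32 | 92% / 93% / 22 |
| Enrolled | within 180 days | 65% / 69% / 38 | 88% / 91% / 28 |
| Enrolled | over one year | 49% / 62% / 47 | 77% / 88% / 38 |
| One year completed | any within the year | 71% / 80% / 41 | 89% / 95% / 35 |

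**4. Failures at once, successes after one year.** The rule now crosses too readily at low risk. At risk 0.05 it does so in 18% of trials (failures uniform over the year) to 31% (within 90 days), against 3.2% stated. At risk 0.10 it does so in 51% to 70%, against 18.5%.

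**5. Accrual rate.** The futility text's 2 per month is 2 × 12 = 24 per year, not 20. At that rate, with N = enrolled, one-year timing and risk 0.25, 71% hold during accrual and mean N is 42.

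**The case against.** Nothing is miscalculated: the table is right for immediate outcomes, and the boundary needs no change. The plan prints an expected sample size, not a number enrolled. If that meant patients evaluated, and N were evaluated patients, both rows would stand. Counting only patients who finish a year also fits poorly with continuous monitoring. The size of the effect rests on assumed timing: the low starting dose and two-weekly laboratory checks in the first 60 days suggest that intolerance may show early, and with failures inside 30 days the gap nearly closes. A crossing after the last entry can still halt treatment, so the ever-crossed percentage is a fair comparator. Finally, crossing triggers a consultation, and the PI and the Safety Monitoring Committee review safety in any case (section 5.2).

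Much of this stands as qualification. This is an unstated model and an undefined N rather than a slip in arithmetic, and the one-year figures are scenarios. It does not remove the point. The text does not say that sample size means evaluated patients, and a rule that holds enrolment is naturally judged by the number enrolled. Hospitalizations count throughout participation, and treatment holds have no time limit (section 3.2.3), so late failures cannot be excluded. On the ever-crossed measure, the enrolled reading with one-year timing still gives 62% against 79.4% at risk 0.20. Committee review limits the harm but neither defines N nor corrects the table.

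**Conclusion.** The concern holds. The printed operating characteristics belong to a design with immediate outcomes, and the plan does not define N.

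- **Enrolled reading:** expected enrolment is understated at the higher risks, and the stopping percentages fall as failures come later. At risk 0.25, every window tested gives a mean above 16.1.
- **Full-follow-up reading:** the percentages hold only if crossings after accrual ends are counted, and enrolment at risk 0.25 is about 35, roughly twice the figure stated.
- **Failures-at-once reading:** the rule over-fires at low risk.

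The direction under the first two readings does not depend on the timing assumption; the size does, from slight at 30 days to more than double at one year (38 / 16.1 ≈ 2.4). The change should be made, but the boundary itself is sound.

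**What to change.** Add one or two sentences stating the period over which a failure counts, when a patient enters N, and how patients still in follow-up are treated. Keep the beta(1, 6) prior and the 0.15/75% rule.

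Re-simulate the table with staggered entry, as the plan already does for futility, using one accrual rate throughout and a range of failure timings. Restate both rows, showing holds during accrual separately from crossings at any time, and label the sample size as enrolled or evaluated.

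Weighting failure-free patients by time on study is an option, but only if the weights reflect when failures are expected. Linear one-year weights give about 17% stopping at risk 0.10 if failures are uniform over the year. If all failures fall within 90 days, they over-hold: about 13%, 40% and 72% at risks 0.05, 0.10 and 0.15, against 3.2%, 18.5% and 49.7% stated.

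The cost is a short simulation and a revised table. The restated sample sizes will look less favourable, and counting only completed patients would delay a hold.

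### The futility table's H0-rejection column does not describe the planned three-year EFS test: under the table's own exponential model that test would almost never reject, against a printed 3% to 96%

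*Combined protocol and SAP*

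**What the plan says.** All of this is in section 6.0 of the combined protocol and SAP unless noted.

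- **Planned test** (Analysis of secondary objectives): "The three-year EFS will be compared to the null EFS of 49% with a Z-score and a one-sided alpha level of 0.05". No other efficacy null is stated anywhere.
- **Simulation model** (Early Stopping Guideline for Futility): "Simulations were carried out with exponential survival and staggered patient entry", and "We assumed, on average, 2 patients would enter the study per month". The table is introduced with "The following tables summarize the operating characteristics under various scenarios for the underlying exponential EFS, based on 1000 simulations".
- **Table**: rows are true one-year EFS of 0.45, 0.50, 0.55, 0.60, 0.65 and 0.70. The last column, "Prob H0 Rejected", reads 0.03, 0.12, 0.28, 0.57, 0.83 and 0.96. Its null, time point and critical value are not given.
- **Historical control**: "the one and three-year EFS for low grade B cell lymphomas was 67 and 49% respectively".
- **Futility rule**: "the stopping rule will hold enrollment if the posterior probability of one-year EFS being less than 50% is 70% or higher", with a beta(3,2) prior and looks at 20 patients and every 10 after that, up to 60.
- **Accrual** (Sample size/Accrual Rate): "The accrual rate for this study is expected to be 20 patients per year".
- **Power** (section 3.2.1): 85% with 60 patients for a rise in EFS from 49% to 69%.

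**The concern.** A table of design operating characteristics with a column for rejecting H0 will normally be read as the chance that the trial's efficacy test succeeds. The one stated efficacy null is 49% at three years. The rows are exponential with one-year EFS no higher than 0.70, which puts three-year EFS far below 49%. A test of that null should then almost never reject, yet the column climbs to 0.96.

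The misreading would be serious. The historical one-year rate of 67% lies between the last two rows, where the column shows 0.83 and 0.96. Someone judging the design could conclude that a regimen no better than history is very likely to be declared active, or that power is excellent at a modest one-year rate. Neither describes the planned test.

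**Working it through.** **1. Three-year EFS implied by each row.** For exponential survival, S(3) = S(1)³. The planned test is then evaluated in two ways.

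*Exact, all 60 followed for three years.* Rejection needs (x/60 − 0.49)/√(0.49 × 0.51/60) > 1.645. The standard error is 0.0645. For x = 36, z = 0.110/0.0645 = 1.70; for x = 35, z = 0.093/0.0645 = 1.45. So at least 36 of 60 must be event-free.

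*Simulated as written.* Exponential EFS, 2 patients per month, looks at 20/30/40/50/60, beta(3,2) prior, enrolment held when P(one-year EFS < 0.50) ≥ 0.70, final Kaplan-Meier Z-test 12 months after last entry. The plan does not define its effective sample size; it is taken here from the Greenwood variance.

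| One-year EFS | Three-year EFS | Printed stop | Simulated stop | Printed H0 rejected | Planned test, simulated | One-year test v 0.49, closed form |
|---|---|---|---|---|---|---|
| 0.45 | 0.091 | 0.60 | 0.62 | 0.03 | 0 | 0.011 |
| 0.50 | 0.125 | 0.37 | 0.39 | 0.12 | 0 | 0.068 |
| 0.55 | 0.166 | 0.17 | 0.17 | 0.28 | 0 | 0.236 |
| 0.60 | 0.216 | 0.07 | 0.07 | 0.57 | 0 | 0.524 |
| 0.65 | 0.275 | 0.02 | 0.02 | 0.83 | 0 | 0.809 |
| 0.70 | 0.343 | 0.01 | 0.01 | 0.96 | 0.001 | 0.960 |

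The simulation reproduces the plan's futility column, so the model is close to the one the plan used. The planned test nevertheless rejects essentially never; repeated runs gave at most 0.3% in any row. The exact calculation agrees: 0.004% at row 0.70 and 0.00001% at row 0.65.

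**2. What the column resembles.** The last column is a one-sided 0.05 test of one-year EFS against 0.49 with n = 60. The critical value is 0.49 + 1.645 × 0.0645 = 0.596. At row 0.65, for example, (0.65 − 0.596)/√(0.65 × 0.35/60) = 0.87, which gives 0.81. The fit is within about 0.05 in every row. A one-year posterior rule, P(EFS > 0.50) > 0.90, fits about equally well, so the exact basis cannot be recovered.

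**3. Rows that are missing.** Under the exponential model, reaching 49% at three years needs one-year EFS of 0.49^(1/3) = 0.788, and reaching 69% needs 0.69^(1/3) = 0.884. Both lie outside the table. The model also contradicts the cited history: 0.67³ = 0.30, not 0.49.

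**4. The planned test on relevant curves.** Null: 67%/49%. Target: 69% at three years. Assuming proportional hazards, HR = ln 0.69/ln 0.49 = 0.52, so one-year EFS is 0.67^0.52 = 0.81. With the futility rule in force:

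| Curve | Final analysis 12 months after last entry, 20/year | Same, 24/year | Complete three-year data (exact, no futility rule) |
|---|---|---|---|
| 67%/49% | 6.8% | 7.7% | 5.7% |
| 81%/69% | 86% | 82% | 95% |

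Across separate simulations the 12-month figures ranged over about 6% to 9% and 82% to 87%. The stated 85% power is thus consistent with the three-year test at one year of added follow-up. It is the table that does not match that test.

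**The case against.** **The table is visibly a one-year table.** Its scenario and estimate columns are labelled one-year, and the text says monitoring uses one-year EFS. That is fair, but it explains the column without repairing it. H0 is undefined, the only stated null is at three years, and a one-year test against about 49% would say little when the historical one-year rate is already 67%.

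**The near-zero figure depends on extending the exponential model to three years, a model that conflicts with the history.** This stands as a qualification. With the historical shape, S(3) = S(1)^1.78 (1.78 = ln 0.49/ln 0.67), the rows map to three-year EFS of 0.24 to 0.53, and only row 0.70 exceeds 49%. Even there, with complete data, (0.53 − 0.596)/√(0.53 × 0.47/60) = −1.03, so the planned test rejects about 15% of the time, against a printed 96%. The column fails to describe the planned test under either shape.

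**The practical effect is small.** EFS is secondary, the futility columns are not shown to be wrong, and the rule itself stops only about 1.4% to 2.3% of trials at 67%/49% and 0.05% or fewer at 81%/69%. This also stands, and it limits the weight of the point. It does not make the printed column correct.

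**The 85% power is reproduced only under particular follow-up assumptions.** True: complete follow-up gives about 95%. The plan does not state the method behind its figure.

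**Conclusion.** The concern holds. The rejection column does not belong to the planned analysis. Under the table's stated exponential model the planned three-year test rejects in 0% to 0.3% of trials in every row, against 3% to 96% printed. That the rows lie below 49% is plain arithmetic. The simulated rates rest on a Greenwood effective sample size and a final analysis 12 months after last entry.

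On the historical 67%/49% curve the planned test rejects about 6% to 9% of the time, where the table would suggest 83% to 96%. Power of about 82% to 87% at 69% also assumes proportional hazards. These are the type I error and power that the table should show and does not. The one-year reading of the column remains an inference.

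A lesser point concerns the futility rationale in section 6.0. It argues for halting when one-year EFS is convincingly below the targeted three-year EFS, which appears to mean the 69% of section 3.2.1, although no passage labels 69% that way. The rule then uses 50%, essentially the three-year null. The 50% rule is disclosed and valid as a bound, but it is not the rule that the rationale describes.

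**What to change.** 1. State at the table which H0, time point and critical value the column uses.
2. Recompute it for the planned three-year Z-test against 49%, with the futility rule in force and a hazard that reproduces 67% at one year and 49% at three. Include a null row (67%/49%) and a target row (about 81%/69%, with proportional hazards stated as an assumption).
3. Use the stated 20 patients per year; the present simulation uses 2 per month, or 24 per year. Define the effective sample size and the timing of the final analysis.
4. If a one-year test was intended, label the column so and say that it is not the planned analysis.
5. Reconcile the futility rationale with the 50% threshold.

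The cost is one simulation rerun and a relabelled table. No planned analysis, sample size or stopping threshold has to change.

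A stricter futility benchmark is a separate, optional choice with a real price. For example, holding enrolment when P(one-year EFS < 0.67) ≥ 0.80 would stop about 40% of trials at 67%/49% and 3% at 81%/69%, but about 26% when one-year EFS is 0.70 and three-year EFS is still 69%. The 67% is also a low-grade B-cell figure, while the trial enrols mixed histologies.
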